Non-interventional Study Protocol

Document Number:	c17261390-04
BI Study Number:	1321-0023
BI Investigational Product(s):	Praxbind™
Title:	Post marketing surveillance program of Praxbind™ use in India.
Brief lay title	Praxbind™ India PMS program
Protocol version identifier:	3.0
Date of last version of protocol:	13 Sep 2017
PASS:	Yes
EU PAS register number:	EUPAS21619
Active substance:	Idarucizumab
Medicinal product:	1 vial of 50 ml contains 2.5 g Idarucizumab (50 mg/ml); Total recommended dose of 5g.
Product reference:	Not Applicable
Procedure number:	Not Applicable
Marketing authorisation holder(s):	
Joint PASS:	No
Research question and objectives:	The main objective of the Praxbind™ administration surveillance program is to evaluate the prescription patterns of use of Praxbind™ in a clinical practice setting, with special focus on ADRs and fatal AEs.

Proprietary confidential information © 2018 Boehringer Ingelheim International GmbH or one or more of its affiliated companies

Country(-ies) of study:	India
Author:	
Marketing authorisation holder(s):	
In case of PASS, add: MAH contact person:	
In case of PASS, add: <EU-QPPV:>	
In case of PASS, add: <Signature of EU-QPPV:>	Signature of EU-QPPV is added at the end of the Protocol in the signature page.
Date:	23 Mar 2018
Page 2 of 41	
Proprietary confidential information © 2018 Boehringer Ingelheim International GmbH or one or more of its affiliated companies. All rights reserved. This document may not - in full or in part - be passed on, reproduced, published or otherwise used without prior written permission	

3. LIST OF ABBREVIATIONS

ADR	Adverse Drug Reaction
AE	Adverse Event
AESI	Adverse Event of Special interest
CA	Competent Authority
CCDS	Company Core Data Sheet
CI	Confidence Interval
CML	Local Clinical Monitor
CRA	Clinical Research Associate
CRF	Case Report Form
CTCAE	Common Terminology Criteria for Adverse Events
CTP	Clinical Trial Protocol
EMA	European Medicines Agency
ENCePP	European Network of Centers for Pharmacoepidemiology and Pharmacovigilance
EU	European Union
FDA	Food and Drug Administration
GCP	Good Clinical Practice
GEP	Good Epidemiological Practice
GPP	Good Pharmacoepidemiology Practice
GVP	Good Pharmacovigilance Practices
IB	Investigator's Brochure
ICF	Informed Consent Form
IEC	Independent Ethics Committee
IRB	Institutional Review Board
MAH	Marketing Authorisation Holder Activities
NIS	Non-Interventional Study
SAE	Serious Adverse Event

4. RESPONSIBLE PARTIES

Contact details and the list of all investigators will be kept in a stand-alone document.

5. ABSTRACT

Name of company: Boehringer Ingelheim India Pvt Ltd			
Name of finished medicinal product: Praxbind™			
Name of active ingredient: Idarucizumab			
Protocol date: 12 Jul 2017	Study number: 1321-0023	Version/Revision: 3.0	Version/Revision date: 23 Mar 2018
Title of study: Post marketing surveillance program of Praxbind™ use in India.			
Rationale and background: Praxbind™ (Idarucizumab) is a humanized monoclonal antibody fragment (Fab) that binds to dabigatran with very high affinity. Praxbind™ potently and specifically binds to dabigatran and its metabolites and neutralises its anticoagulant effect. Praxbind™ is a specific reversal agent for dabigatran and is indicated in patients treated with dabigatran etexilate when rapid reversal of the anticoagulant effects of dabigatran is required: 
• for emergency surgery/urgent proceduresOR• in life-threatening or uncontrolled bleeding. The aim of this Praxbind™ drug administration surveillance program is to collect data on Praxbind™ prescription patterns in a clinical practice setting in India.			
Research question and objectives: The main objective of the Praxbind™ drug administration surveillance program is to evaluate the prescription patterns of use of Praxbind™ in a clinical practice setting, with special focus on ADRs and fatal AEs.			
Study design: This drug administration surveillance program is designed as an Indian multi-Center program enrolling patients administered with Praxbind™ after launch. There are no protocol mandated follow-up visits or procedures associated with the program. No interference with usual medical care is involved, and thus it will not affect the treatment of patients. The program will apply to all participating Centers where the Praxbind™ is prescribed depending on market country regulations and requirements.			

Name of company: Boehringer Ingelheim India Pvt Ltd			
Name of finished medicinal product: Praxbind™			
Name of active ingredient: Idarucizumab			
Protocol date: 12 Jul 2017	Study number: 1321-0023	Version/Revision: 3.0	Version/Revision date: 23 Mar 2018

Praxbind™ is prescribed depending on market country regulations and requirements.
			
Population:	
Hospital (sites) with access to Praxbind™ will receive information material about the drug administration surveillance program. The target population will be all patients, who receive Praxbind™ as prescribed by the treating physician.
 
This program will be initiated after the commercial availability of Praxbind™ in India. It will include up to 25 patients who require Praxbind™ as prescribed according to the approved Indian label or the patients included in 2 years at selected Centers approved by the regulatory authority, whichever is earlier.
 
The patients who participate in 1160.189 and 1160.248 study and have a requirement for Praxbind™ will also be part of this protocol.
 
Inclusion criteria:
 
1. Patients treated with Pradaxa (dabigatran etexilate) capsules with requirement of rapid reversal of the anticoagulant effects of dabigatran:
• For emergency surgery/urgent procedures (or)• In life-threatening or uncontrolled bleeding2. Written informed consent in accordance with International Conference on Harmonization Good Clinical Practice (GCP) guidelines and local legislation and/or regulations. 
Exclusion criteria:
 
• Participation in an Praxbind™ clinical trial		

Name of company: Boehringer Ingelheim India Pvt Ltd			
Name of finished medicinal product: Praxbind™			
Name of active ingredient: Idarucizumab			
Protocol date: 12 Jul 2017	Study number: 1321-0023	Version/Revision: 3.0	Version/Revision date: 23 Mar 2018
Variables:	
Information on basic patient characteristics and use of Praxbind™ will be entered into the Praxbind™ drug administration record. The following anonymized data will be collected from the Praxbind™ administration records upon availability:
 
1. Site characteristics
 
• Multi-specialty hospitals with emergency management facilities and having access to Praxbind™.• Practice type (academic, non-academic, private, Government);• Availability of prescription/medical records at the site. 
2. Patient data
 
• Year of birth• Gender: Male or Female• Vital Signs• Physical Examination• Laboratory data• Pregnancy status in case of female patient 
3. Medical History
 
• Name, dose and last intake of previous anticoagulant medications (Dabigatran);• Pertaining to haemorrhagic risk factors or impact on safety outcomes (e.g. renal impairment, congenital or acquired coagulation disorders, thrombocytopenia or functional		

Name of company: Boehringer Ingelheim India Pvt Ltd			
Name of finished medicinal product: Praxbind TM			
Name of active ingredient: Idarucizumab			
Protocol date: 12 Jul 2017	Study number: 1321-0023	Version/Revision: 3.0	Version/Revision date: 23 Mar 2018

Platelet defects, recent biopsy, recent surgery, major trauma, bacterial endocarditis, esophagitis, gastritis, gastroesophageal reflux, hepatic disorders, vascular disorders, neoplasms/cancer, inherited vascular disorder (aneurysms, arteriovenous malformation, microangiopathy) and the HAS-BLED score).
 
Concomitant treatment pertaining to haemorrhagic risk factors or impact on safety outcomes (e.g. acetylsalicylic acid, non-steroidal anti-inflammatory drugs, clopidogrel, selective serotonin reuptake inhibitors or serotonin–norepinephrine reuptake inhibitors, sStrong P-Gp inhibitors (e.g. ketoconazole, clarithromycin, ticagrelor), chemotherapy, radiation therapy. 
3. PraxbindTM utilization
 
Department (emergency, operating room, ICU, other patient setting);Type of surgery / procedure if applicable;Information on bleeding event (pre and post PraxbindTM administration) including location (Gastrointestinal tract; Intracranial; Skin, Urogenital tract, Intramuscular, Retroperitoneal, Undefined location, Other defined location) if applicable, and if bleeding was life threatening (yes/no);Indication: life-threatening or uncontrolled bleeding requiring urgent medical intervention, emergency surgery or other urgent medical procedure necessitating rapid reversal of the anticoagulant effect of dabigatran prior to surgery/procedure, scheduled or planned surgery/procedure,			

Name of company: Boehringer Ingelheim India Pvt Ltd			
Name of finished medicinal product: Praxbind TM			
Name of active ingredient: Idarucizumab			
Protocol date: 12 Jul 2017	Study number: 1321-0023	Version/Revision: 3.0	Version/Revision date: 23 Mar 2018

• Dosage and administration (total dose administered and time interval between the administration of the two vials; vials to be taken one after the other, immediate administration of the second vial is mandatory).• Premature PraxbindTM administration discontinuation (yes/no).• In case if the patient requires an additional 5 g dose for the following conditions as per the label:• recurrence of clinically relevant bleeding together with prolonged clotting times, or• if potential re-bleeding would be life-threatening and prolonged clotting times are observed, or• patients require a second emergency surgery/urgent procedure and have prolonged clotting times.• Information on restart of anticoagulation therapy (which anticoagulation treatment including dose and when was it restarted).• All adverse drug reactions (ADRs, serious and non-serious) associated with PraxbindTM,• All AEs with fatal outcome in patients exposed to PraxbindTM			

Name of company: Boehringer Ingelheim India Pvt Ltd			
Name of finished medicinal product: Praxbind™			
Name of active ingredient: Idarucizumab			
Protocol date: 12 Jul 2017	Study number: 1321-0023	Version/Revision: 3.0	Version/Revision date: 23 Mar 2018
Outcomes	
Primary Outcome:- Any suspected ADRs and fatal AEs; with special focus on hypersensitivity and thrombotic event, occurred within 7 days after Praxbind™ administration.
 
Secondary Outcome:- Percentage of patients who either received Praxbind™ for emergency surgery/urgent procedures or in life-threatening or uncontrolled bleeding at the end of 2 years.
		
Data sources:	Data collected will be entered by the site using electronic CRF forms. It is the doctor's responsibility to ensure the accuracy of the data provided to the program by any site staff that is trained for the program data collection.		
Study size:	This program will be initiated after the commercial availability of Praxbind™ in India. It will include up to 25 consecutive patients who may require Praxbind™ prescribed according to the approved Indian label or the patients included in 2 years at selected Centers approved by the regulatory authority, whichever is earlier.		
Data analysis:	A detailed analysis plan will be prepared prior to First Patient In. All variables will be presented using descriptive statistics (absolute and relative frequencies, means, standard deviations, medians, quartiles, minimum and maximum values, 95% CIs) as appropriate for the nature of the variables (i.e. categorical or continuous).		
Milestones:	
Start of data collection: Currently planned for Q2 2018 (Depending on start time of commercial availability and necessary regulatory approvals). End of data collection: Currently planned for Q2 2020 (As per the DCGI approval of marketing authorization).
 
Final report: Currently planned for Q3 2020 (Depending on completion of data collection).
		

6. AMENDMENTS AND UPDATES

Following administrative were performed throughout the document:-

Sr No	Section	Page no.	Protocol V 3.0 dated 23 Mar 2018
1	Title Page	1	EU PAS Register Number added (EUPAS21619)
2	Abstract: Milestones	13	Start of data collection: Currently planned for Q4 Q2 2018 (Depending on start time of commercial availability and necessary regulatory approvals). End of data collection: Currently planned for Q4 Q2 2020 (Depending on start of market authorisation and Praxbind™ usage. As per the DCGI approval of marketing authorization). Final report: Currently planned for Q3 2020 (Depending on start of market authorisation and Praxbind™ usage-completion of data collection).
3	Section 7:- Milestones	16	Final Protocol 13 Sep 2017 (Revision) 12 Jul 2017 Start of data collection: 15 Dec 2017 Q 2 2018 End of data collection: 15 Dec 2019 Q 2 2020 Final report of study results: 30 Feb 2020 Q 3 2020 Added:- Revision 1.0 (Version 2.0) 13 Sep 2017 Revision 2.0 (Version 3.0) 23 Mar 2018
4	Abstract:- Population; Section 10.1.2:- Study Population	8; 19	The patients who participate in 1160.189 and 1160.248 study and have a requirement for Praxbind™ will also be part of this protocol.
5	ENCePP Checklist for Study Protocols: Section 1. Milestones	37	Comment deleted:- 1.1.5 EU PAS Registration will be completed after the Protocol is finalized. Updated:- EU PAS registration completed and number added in the title page.

Typographical errors corrected throughout the document.

The following additions have been made to the Protocol based on the recommendations of the Drug Controller General India, DCG(I):-

Sr. No	Section	Page no.	Protocol V 2.0 dated 13 Sep 2017
1	Title Page; Abstract and Section 9:-Research question and objectives	1, 7 and 17	The main objective of the Praxbind® administration surveillance program is to evaluate the prescription patterns of use of Praxbind® in a clinical practice setting, with special focus on ADRs and fatal AEs.
2	Abstract:-Outcomes; Section 10.2.2.1:- Primary Outcomes	12 and 21	Any suspected ADRs and fatal AEs; with special focus on hypersensitivity and thrombotic event, occurred within 7 days after Praxbind® administration.
3	Abstract:-Outcomes; Section 10.2.2.2:- Secondary Outcomes	12 and 21	Percentage of patients who either received Praxbind® for emergency surgery/urgent procedures or in life-threatening or uncontrolled bleeding at the end of 2 years.

Following administrative and typographical corrections were performed throughout the document:-

Sr No	Section	Page no.	Protocol V 2.0 dated 13 Sep 2017
1	Medicinal Product	1	1 vial of 50 ml contains 2.5 g Idarucizumab (50 mg/ml); Total recommended dose of 5g.
2	Section 7:- Milestones	18	Updated as per the new planned dates
3	Abstract:- Population; Section:-10.1.2 Study population	8, 18	The target population will be all patients, who receive Praxbind® as prescribed by the treating physician. It will include up to 25 consecutive patients who require Praxbind® as prescribed according to the approved Indian label or the patients included in 2 years at selected Centers approved by the regulatory authority, whichever is earlier.
4	Abstract:-Variables; Section 10.2:- Variables	9, 19	Availability of prescription/medical records at the pharmacy site.
5	Abstract:-Variables; Section 10.2:- Variables	9, 19	• Pregnancy status in case of female patient.

6	Abstract:-Variables; Section 10.2:- Variables	11, 20	
All adverse drug reactions (ADRs, serious and non-serious) associated with Praxbind™,All AEs with fatal outcome in patients exposed to Praxbind™
7	Section 10.1 Study Design	18	This is a post marketing surveillance study wherein patients will be eligible for the study if they are prescribed Praxbind® as per the approved label. The drug administration surveillance program is designed as a multi-center program enrolling patients administered with Praxbind®.
8	10.1.2 Study population	18	The target population will be all patients, who receive Praxbind® prescribed as per the approved label.
9	10.1.3 Study discontinuation	19	The investigator / the study site will be reimbursed for reasonable expenses incurred in case of study termination (except in case of the third reason).
10	10.9.2. Study Records	22	Case Report Forms (CRFs) for individual patients will be provided by the sponsor electronically.
11	10.7 Quality Control	22	It is the responsibility of the pharmacist Investigator to ensure that the data are as accurate and complete as possible. The Pharmacist Investigator and delegate will be trained on data entry.
12	12.1. Definition of adverse events	26	Any suspected transmission via a medicinal product of an infectious agent is also considered a serious adverse reaction.

- Name of study drug changed from Idarucizumab to Praxbind™ across the entire Protocol.

7. MILESTONES

Milestone	Planned Date
Final Protocol	12 Jul 2017
Revision 1.0 (Version 2.0)	13 Sep 2017
Revision 2.0 (Version 3.0)	23 Mar 2018
Start of data collection	Q2 2018
End of data collection	Q2 2020
Final report of study results:	Q3 2020

8. RATIONALE AND BACKGROUND

A clinical development program is ongoing to support marketing authorisation submissions for Praxbind™ indicated in patients treated with dabigatran who require emergency surgery/urgent procedures or who have a life-threatening or uncontrolled bleeding when rapid reversal of the anticoagulant effects of dabigatran is required.

The aim of this drug administration surveillance program is to capture a large proportion of the patients treated with Praxbind™ in order to collect data on Praxbind™ prescription patterns in a clinical practice setting in India.

Praxbind™ (Idarucizumab) is a humanized monoclonal antibody fragment (Fab) that binds to Dabigatran with very high affinity. Praxbind™ potently and specifically binds to dabigatran and its metabolites and neutralises its anticoagulant effect. Praxbind™ is a specific reversal agent for dabigatran and is indicated in patients treated with dabigatran etexilate when rapid reversal of the anticoagulant effects of dabigatran is required:

- for emergency surgery/urgent procedures
- (or)
- in life-threatening or uncontrolled bleeding

Dabigatran etexilate (Pradaxa) is an oral pro-drug of dabigatran, a direct-acting thrombin inhibitor that has been shown to be effective in the prevention or reduction of thrombotic events in:

- patients with non-valvular atrial fibrillation
- patients with deep vein thrombosis or pulmonary embolism who have been treated with a parenteral anticoagulant for 5-10 days
- patients who have previously received anticoagulant therapy for treatment of venous thromboembolism
- in orthopedic surgery patients at risk for post-operative DVT

Anticoagulation therapy is a mainstay of treatment and prevention of pathologic thrombosis in these different clinical settings. However, as with all anticoagulants, bleeding is a potential side effect. The risk of bleeding in dabigatran-treated patients during emergency surgery or other urgent invasive procedures is also a consideration.

9. RESEARCH QUESTION AND OBJECTIVES

The main objective of the PraxbindTM drug administration surveillance program is to evaluate the prescription patterns of use of PraxbindTM in a clinical practice setting, with special focus on ADRs and fatal AEs.

10. RESEARCH METHODS

This program will be initiated after the commercial availability of Praxbind™ in India. It will include patients administered with Praxbind™ into the surveillance program after commercial availability in 2 years at selected centers approved by the regulatory authority.

10.1 STUDY DESIGN

This is a post marketing surveillance study wherein patients will be eligible for the study if they are prescribed Praxbind™ as per the approved label. The drug administration surveillance program is designed as a multi-center program enrolling patients administered with Praxbind™. Data will be collected for patients who have been treated with Praxbind™ within 2 years. There are no protocol mandated follow-up visits or procedures associated with the program. No interference with usual medical care is involved, and thus it will not affect the treatment of patients.

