10.2.2 Outcomes

10.2.2.1 Primary outcomes

Any suspected ADRs and fatal AEs; with special focus on hypersensitivity and thrombotic event, occurred within 7 days after PraxbindTM administration.

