10.9.2.1 Source documents

Source documents provide evidence for the existence of the patient and substantiate the integrity of the data collected. Source documents are filed at the investigator's site.

Data reported on the e-CRFs that are transcribed from source documents must be consistent with the source documents or the discrepancies must be explained. The investigator may need to request previous medical records or transfer records, depending on the study; also current medical records must be available.

For e-CRFs, the following data need to be derived from source documents:

- Patient identification (gender, date of birth)
- Patient participation in the study (product, study number, patient number, date patient was informed)
- Dates of Patient's visit, (including Praxbind™ administration & Hospital Admission details)
- Medical history (including indication and concomitant diseases, if applicable)
- Medication history
- Adverse events (onset date (mandatory), and end date (if available))
- Serious adverse events (SAEs) (onset date (mandatory), and end date (if available))
- Concomitant therapy (start date, changes)
- Laboratory results
- Conclusion of Patient's Participation in the study

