11.1 STUDY APPROVAL, PATIENT INFORMATION, AND INFORMED CONSENT

In addition to review and approval by Drug controller general of India (DCGI), the approval of Institutional Review Board (IRB) or Ethics Committee will be sought as per the institutional procedures before the start of this active surveillance.

Prior to patient participation in this active surveillance study, written informed consent must be obtained from each patient (or the patient's legally accepted representative) according to the regulatory and legal requirements of India. Each signature must be personally dated by each signatory and the informed consent and any additional patient-information form retained by the Investigator as part of the study records. A signed copy of the informed consent and any additional patient information must be given to each patient or the patient's legally accepted representative.

The Investigator must give a full explanation to the participants of this active surveillance regarding the collection of the safety data at specific time points. The Investigator obtains written consent of the patient's own free will with the informed consent form after confirming that the patient understands the contents. The Investigator must sign and date the informed consent form.

The patient must be informed that his/her personal study-related data will be used by Boehringer Ingelheim in accordance with the local data protection law. The level of disclosure must also be explained to the patient.

The patient must be informed that his / her medical records may be examined by authorized monitors (CML/CRA) or Quality Medicine auditors appointed by Boehringer Ingelheim, by appropriate IRB / IEC members, and by inspectors from regulatory authorities.

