12.2 ADVERSE EVENT AND SERIOUS ADVERSE EVENT COLLECTION AND REPORTING

The investigator shall maintain and keep detailed records of all AEs in their patient files.

Collection of AEs

The study design is of non-interventional nature and the study is conducted within the conditions of the approved marketing authorization. Sufficient data from controlled interventional trials are available to support the evidence on the safety and efficacy of the studied BI drug. For this reason the following AE collection and reporting requirements have been defined.

The following must be collected by the investigator in the (e) CRF from signing the informed consent onwards until the end of the study:

- all adverse drug reactions (ADRs, serious and non-serious) associated with PraxbindTM,
- all AEs with fatal outcome in patients exposed to PraxbindTM.

All ADRs, including those persisting after study completion must be followed up until they are resolved, have been sufficiently characterized, or no further information can be obtained.

The investigator carefully assesses whether an AE constitutes an ADR using the information below.

Causal relationship of adverse event

The definition of an adverse reaction implies at least a reasonable possibility of a causal relationship between a suspected medicinal product and an adverse event. An adverse reaction, in contrast to an adverse event, is characterized by the fact that a causal relationship between a medicinal product and an occurrence is suspected.

Medical judgment should be used to determine the relationship, considering all relevant factors, including pattern of reaction, temporal relationship, de-challenge or re-challenge, confounding factors such as concomitant medication, concomitant diseases and relevant history.

Arguments that may suggest a **reasonable causal relationship** could be:

- The event is **consistent with the known pharmacology** of the drug
- The event is known to be caused by or **attributed to the drug class**.
- **A plausible time to onset of the event** relative to the time of drug exposure.
- Evidence that the **event is reproducible** when the drug is re-introduced
- **No medically sound alternative etiologies** that could explain the event (e.g. preexisting or concomitant diseases, or co-medications).

- The event is typically **drug-related and infrequent in the general population** not exposed to drugs (e.g. Stevens-Johnson syndrome).

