## **7.6 HANDLING OF MISSING DATA AND OUTLIERS**

No missing data analysis is planned for this study. Missing values will be considered as missing, no imputation will be done for the analysis purpose.

Missing or incomplete AE dates are imputed according to BI standards  (i.e. “Handling of missing and incomplete AE dates”).

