## **7.7 BASELINE, TIME WINDOWS AND CALCULATED VISITS**

Data will be collected for patients who have been treated with Praxbind within 2 years. No formal visits are planned for this surveillance also there is no protocol mandated follow-up visits or procedures associated with the program.

Last non missing values observed prior to receiving the PraxbindTM will be considered as Baseline value.

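### The 7-day primary outcome is reported on all treated patients, but nothing in the plan shows who was observed to day 7 or says how incomplete observation is handled

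*Protocol*

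**What the plan says.** - **Outcome.** Protocol 10.2.2.1 defines the primary outcome as suspected ADRs and fatal AEs, "with special focus on hypersensitivity and thrombotic event, occurred within 7 days after" administration. SAP 6.1 and 8.4 repeat this; 8.4 adds no estimator.
- **Follow-up.** Protocol 10.1: "There are no protocol mandated follow-up visits or procedures associated with the program". SAP 7.7, the section for time windows, sets no day-7 window: "No formal visits are planned for this surveillance also there is no protocol mandated follow-up visits or procedures associated with the program".
- **Collection duty.** Protocol 12.2 requires the investigator to collect all ADRs and all fatal AEs "from signing the informed consent onwards until the end of the study". Serious ADRs and fatal AEs are reportable within 24 hours and non-serious ADRs within 7 calendar days.
- **Data items.** The variable lists in Protocol 10.2 and SAP 6.4 draw on administration records as far as available. They include no discharge or transfer date, no date last observed and no day-7 status. Protocol 10.9.2.1 adds AE onset dates (mandatory), admission details and "Conclusion of Patient's Participation in the study", the last without a date or a link to day 7.
- **Denominator.** SAP 7.3 and its table of patient sets put the primary outcome on the Treated Set, with no condition on observation. SAP 8.8.1 reports numbers and percentages of patients.
- **Missing data.** SAP 7.6: "No missing data analysis is planned for this study". Missing values stay missing; only AE dates are imputed.

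**The concern.** A percentage with event within 7 days has a plain meaning only if each patient's status at day 7 is known, or if the analysis allows for those whose status is not. Here the dataset records events. A patient followed to day 7 without an event and a patient last seen on day 2 leave the same trace, namely no event record. The rule that missing values stay missing does not help, because an unobserved event produces no record that could be flagged as missing.

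The primary safety percentage of a study capped at 25 patients is at stake, where one event moves the result by 1/25 = 4 percentage points. A reader of the report could not tell a complete 7-day result from one with several patients unobserved for part of the window.

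**Working it through.** The plan has no figure to reproduce: 25 is a cap without a calculation behind it, and no event, discharge or transfer rate is given. The check is therefore a reading of the text, followed by illustrations under stated assumptions.

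**Step 1: what following the plan produces.** Numerator: Treated Set patients with a recorded ADR or fatal AE with onset within 7 days (onset dates are mandatory, so recorded events can be placed in the window). Denominator: the whole Treated Set. A patient who leaves before day 7 without a recorded event contributes 0 to the numerator and 1 to the denominator. An event that never reaches the site can lower the numerator but not raise it, so the effect has one direction.

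**Step 2: bounds.** Assume 25 treated, 2 recorded events and m patients without an event whose day-7 status is unknown. The reported value is 2/25 = 8.0% (exact 95% interval 1.0% to 26.0%) whatever m is. The worst case is (2 + m)/25:

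| m | Worst case |
|---|---|
| 3 | 5/25 = 20.0% |
| 5 | 7/25 = 28.0% |
| 10 | 12/25 = 48.0% |

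**Step 3: expected understatement.** Let f be the share of patients not observed to day 7 and s the share of their 7-day risk that falls after they leave and goes unreported. If leavers and stayers have the same total 7-day risk, reported/true = 1 − f·s.

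| f | s | Ratio | A true 10% shows as |
|---|---|---|---|
| 0.10 | 0.25 | 0.975 | 9.75% |
| 0.20 | 0.50 | 0.90 | 9.0% |
| 0.40 | 1.00 | 0.60 | 6.0% |

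Both f and s are assumptions. If leavers are at lower risk the loss is smaller; if they are sicker (transfers, for instance) it is larger.

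**Step 4: precision with no events.** The exact two-sided 95% upper limit is 1 − 0.025^(1/n): 13.7% for n = 25, 16.8% for n = 20 and 21.8% for n = 15. Quoting 13.7% when only 20 were observed to day 7 overstates what was learned.

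**Step 5: which alternative estimate.** With 2 events and 5 patients leaving event-free, the proportion among those observed to day 7 or with an earlier event is 2/20 = 10.0%. It keeps every early event and drops event-free leavers, so it is biased upward. A Kaplan-Meier estimate credits the time that leavers were observed. If both events precede all departures it gives 1 − 23/25 = 8.0%; if both follow them, 1 − (19/20)(18/19) = 10.0%; otherwise it lies between.

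**The case against.** Protocol 12.2 is the strongest reply. The duty to collect ADRs and fatal AEs runs from consent to the end of the study, with prompt reporting, so it does not stop when the patient leaves hospital. Protocol 10.9.2.1 also lists an end-of-participation item, and the CRF itself (version 3.0, cited in SAP section 4) is not among the documents; it may already hold a date. This stands, and it rules out one tempting inference, that safety collection ends at discharge or that no end of observation is recorded at all. But the duty defines no end for the individual patient, requires no contact after discharge, and does not make the site document that day 7 was reached. The end-of-participation item is not tied to day 7, and the SAP does not use it.

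A reader might also infer that the plan classifies early leavers as event-free. No section says so. It is the arithmetic default when recorded events are divided by everyone treated. Nor do the documents show that the result will be materially biased: if nearly all patients stay in hospital for 7 days, or late events reach the site through the reporting duty, the loss may be close to nil.

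Protocol 11.1 tells the investigator to give an explanation "regarding the collection of the safety data at specific time points", and no such points are defined. That is a wording inconsistency and not evidence of bias.

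Finally, the study is descriptive, its main objective is prescription patterns, and it is non-interventional by design. This limits the consequences, but the 7-day safety outcome is still the primary one, and the remedy adds no visit or test.

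**Conclusion.** The point holds in this form: a 7-day primary outcome is reported on all treated patients, with nothing listed that shows observation to day 7 and no analysis rule for those without it. By default, unobserved time counts as event-free, so incomplete observation can only understate the 7-day percentage. The documents do not allow the amount to be computed. Under the assumptions in the working, reported/true risk runs from 0.975 to 0.60, and 2 events in 25 with 5 unobserved gives 8.0% reported against a 28.0% worst case. These figures illustrate sensitivity and do not predict this study's result. The study remains feasible, but the primary safety percentage cannot be properly interpreted until the number observed to day 7 is known. If follow-up turns out to be complete, the added items will show it.

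**What to change.** 1. **Data.** Record from existing notes or routine contact (a) the date last observed or known alive and (b) the day-7 status: event, no event or unknown. If the end-of-participation item already holds a date, use it for (a). No visit or procedure is added.
2. **SAP 8.4.** State the number observed to day 7; give the primary percentage on the Treated Set with an exact 95% interval (Protocol 10.6.1 provides for 95% CIs; the SAP's general rules for categorical data list only frequency and percentage); and give a worst-case bound that counts unknowns as events.
3. **If an estimate allowing for incomplete observation is wanted,** use a method that censors at the last observed date: Kaplan-Meier at day 7 for the composite, or cumulative incidence where a component is analysed and death competes with it. State that this assumes leaving is unrelated to later risk, which may not hold here. A proportion among patients observed to day 7 or with an earlier event should be labelled as biased upward.
4. **Wording.** Align Protocol 11.1 with the actual collection schedule.

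The cost is one or two data fields, a few table rows and less favourable stated precision: with no events, for example, an upper limit of 16.8% on 20 observed patients instead of 13.7% on 25.
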